### **Primary Outcomes:**

*Conners Adult ADHD Rating Scale-Self Report – Long Version (CAARS-S:L):* The CAARS-S:L is a 66-item rating scale designed to assess ADHD symptoms in adults. The scale contains multiple subscales to assess DSM-IV specified ADHD criteria as well as other facets of ADHD such as inattention/memory problems, hyperactivity/restlessness, impulsivity/emotionality, and problems with self-concept. The scale has good internal consistency (Cronbach's alpha .86-.92) and test-retest reliability (Pearson's  $r = 0.89$ ) (Erhardt et al., 1999).

*Adult ADHD Self-Report Scale (ASRS):* The Adult ADHD Self-Report Scale (ASRS) Version 1.1 is an 18-item scale designed to screen for adult ADHD in community samples. The ASRS was developed by a World Health Organization (WHO) work group in conjunction with the creation of the WHO World Mental Health (WMH) Survey Initiative version of the WHO Composite International Diagnostic Interview (WMH-CIDI).

## **Secondary Outcomes:**

**Risk Task:** The risk aversion task is designed to probe different aspects of reward valuation and decision-making. The task involves making hypothetical binary decisions regarding reward contingencies. Variables in these choices will include probability of reward (uncertainty/ambiguity discounting) and the risk of losing previously earned rewards (risk discounting) (task duration: ~10 min).

**Continuous Performance Task (CPT):** The CPT is a measure of sustained attention. In this task, participants are shown a series of stimuli (letters, numbers, or pictures) on a computer screen and are asked to press the spacebar in response to certain stimuli, but to withhold responding to other stimuli. (task duration: ~15-20min).

**Paced Auditory Serial Addition Task (PASAT):** The PASAT is a validated measure of attention, working memory, and information processing. Subjects are presented aurally with single digit numbers and instructed to respond verbally with the sum of the two most recently presented numbers. The PASAT has been used to assess cognitive impairment in patients with a wide range of neuropsychological conditions and shows a high level of internal consistency and test-retest reliability (Tombaugh, 2006); improvements in performance on the PASAT have been demonstrated following tDCS with working memory training in healthy subjects (Gill et al., 2015).

**Quick Inventory of Depressive Symptomatology (QIDS):** The 16 item QIDS – Self Rated Version (QIDS-SR) (Rush et al., 2003) will be used to assess the severity of depressive symptoms. The QIDS-SR assesses nine diagnostic symptom domains used to characterize a major depressive episode and is sensitive to change resulting from medications, psychotherapy, or somatic treatments.

## **2. Statistical Analysis**

**General Issues:** Prior to performing analyses, standard data screening/cleaning procedures will be applied. These procedures will (a) screen the data for data-entry errors, (b) check for outliers, (c) assess the extent and pattern of missing data, (d) create all summary scores needed for analysis, and (e) check that appropriate distributional assumptions are met. In all analyses, the assumptions underlying the application of all the statistical methods that are used will be examined, principally through the use of standardized residuals, influence diagnostics, and graphical displays. All analyses will be conducted using Stata software (STATA Corporation, College Station, Texas).

**Hypothesis Testing:** The primary outcomes will be cognitive performance on the tasks administered before and after TMS. All of these outcome measures are continuous, and hypotheses will be tested using mixed effects modeling. A sample size of 30 individuals will provide ~80% power to detect a moderate to large effect size, similar to the effect size seen for TMS treatment of depression.

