3. BrAC assessment. See breath alcohol concentration under screening/covariates for exclusionary criteria;

4. Provide information regarding recent nicotine and caffeine intake, and any medication changes since the Intake visit;
5. A carbon monoxide (CO) breath sample (smokers only);
6. Complete paper and pencil questionnaires (POMS);
7. Complete computerized cognitive tasks which may include assessments of working memory, sustained attention, risk aversion, delay discounting or reaction time.

**TMS Sessions (Sessions 1 - 20):** (Visit duration ~1-2hrs). The stimulation protocol is adapted from TMS Investigations of Cognition and Motor Function, which was employed in The Laboratory for Cognition and Neural Stimulation (LCNS).

Participants will complete the following during Sessions 1 - 20:

1. Urine drug screen (Sessions 1, 5, 10, 15 & 20). See key exclusionary criteria; Alcohol/Drugs;
2. Pregnancy screen (females of child bearing potential only) (Sessions 1, 5, 10, 15 & 20);
3. BrAC assessment. See breath alcohol concentration under screening/covariates for exclusionary criteria;
4. Assessment of recent nicotine and caffeine intake, and any medication changes since last assessment (Sessions 1, 5, 10, 15 & 20);
5. TMS safety & side effects questionnaire;
6. A carbon monoxide (CO) breath sample (smokers only);
7. Complete paper and pencil questionnaires;
8. Receive 26 minutes of TMS (active or sham);
9. Complete computerized cognitive tasks which may include assessments of working memory, sustained attention, risk aversion, delay discounting or reaction time (Sessions 5, 10, 15 & 20).

**Attendance:** Participants will be asked to attend all study visits. Participants attending less than 4/5 visits during the first two weeks or less than 3/5 sessions in the final two weeks of the study will be excluded.

**TMS Training Procedures:** Prior to each TMS session an investigator or trained research assistant will review the procedures, goals, risks, and potential benefits of the study and confirm that no change has occurred affecting study inclusion and exclusion criteria. The TMS sessions will be conducted by a trained TMS clinician using the The MagPro R30 (Magventure, Inc., Copenhagen, Denmark) device with a figure 8 coil. During Sessions 1 - 20 participants will receive 26 minutes of sham or active TMS using the parameters described below. Participants will be blind to condition.

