**Table 1. Measures and Time Points**

Activity	Intake	Baseline	TMS Sessions (1 - 20)
Weeks	-1	0	1, 2, 3 & 4
Urine Drug Screen	x	x	x 
Urine Pregnancy Screen	x	x	x 
BrAC	x	x	x
Carbon Monoxide (CO)	x 	x 	x 
Demographics	x		
ETOH History	x		
Smoking Behavior (FTND)	x 		
Caffeine & nicotine use	x	x	x 
Height	x		
Weight	x		
Medical History Form	x		
TMS safety checklist	x		x
ShIPLEY Institute of Living Scale (IQ)	x		
SCID-5	x		
Treatment			
TMS (active or sham)			x
Primary Outcomes			
CARRS: S-L	x	x	x 
ASRS	x	x	x 
Secondary Outcomes			
PASAT		x	x 
Continuous performance task		x	x 
Risk Task		x	x 
QIDS	x	x	x 

 Smokers reporting having smoked in the past 24hrs.

 Administered at sessions 1, 5, 10, 15 & 20.

 Administered at sessions 1, 5, 10, & 15.

 The cognitive battery & ADHD clinical measures will only be administered at TMS sessions 5, 10, 15 & 20.

**Back-up scheduling for Session 1 visits:** Since we are limited in the number of study tracks we are able to run per week we are also offering the opportunity to become a back-up participant for Session 1 visits. Back-up participants will only be scheduled for a TMS session 1 visit (occurring on Mondays). Participants may only be a back-up if they have not yet initiated a TMS track (have not attended TMS Session 1). Becoming a back-up is completely voluntary and participants will not receive any extra stimulation sessions if they decide to become a back-up participant in this study. In order to be scheduled as a back-up participant the participant must agree to do the following:

- Show up for the scheduled Session 1 appointment at the designated time;
- Be available for all subsequent study track visits in the event that they are promoted to the primary participant (if the primary participant for that date does not attend their session or is deemed ineligible at the visit).

If the participant attends the Session 1 visit as a back-up participant and is not needed on that date they will not undergo any study procedures (will not receive any stimulation), they will be

compensated \$25 for their time and will be free to leave. Back-up participants will then be scheduled for the next available study track as the primary participant.

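### The analysis section makes the cognitive tasks primary, while Table 1 and the outcome sections make CAARS-S:L and ASRS primary; no primary score is named under either version

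*Combined protocol and SAP*

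**What the plan says.** Two versions of the primary outcome stand in the current text.

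- **Cognition.** Statistical Analysis, Hypothesis Testing: "The primary outcomes will be cognitive performance on the tasks administered before and after TMS".
- **Symptoms.** In Table 1 the heading "Primary Outcomes" stands over the CAARS-S:L and ASRS rows, and "Secondary Outcomes" over PASAT, the continuous performance task, Risk Task and QIDS. The two outcome sections after the table make the same split.

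Neither version identifies a score. Of CAARS-S:L the Primary Outcomes section says "The scale contains multiple subscales to assess DSM-IV specified ADHD criteria as well as other facets of ADHD", without choosing one, and it names no ASRS score. For the Risk Task, "Variables in these choices will include probability of reward (uncertainty/ambiguity discounting) and the risk of losing previously earned rewards", which points to two discounting measures. No score is given for PASAT or CPT. The battery itself is left open in Procedures (Baseline item 7; TMS Sessions item 9): "Complete computerized cognitive tasks which may include assessments of working memory, sustained attention, risk aversion, delay discounting or reaction time". Delay discounting and reaction time appear in neither Table 1 nor the Secondary Outcomes section.

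The sample-size sentence says that 30 individuals "will provide ~80% power to detect a moderate to large effect size, similar to the effect size seen for TMS treatment of depression". It does not say which outcome this refers to.

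**The concern.** The primary outcome determines which result the trial reports as its answer. Here the only paragraph that describes hypothesis testing contradicts the table and sections that list the outcomes. With both versions in the plan, a favourable result on symptoms or on cognition could be presented as the prespecified primary finding. Within either set, the choice of subscale, task or derived variable is also open.

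The power claim inherits the problem. Detectable effect depends on how strongly the baseline value predicts the final one, and that differs between outcomes. Without a named outcome, effect size, alpha, allocation ratio or baseline correlation, the figure of about 80% can be neither confirmed nor refuted.

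**Working it through.** **1. The texts side by side**

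| Place | Symptom scales | Cognitive tasks |
|---|---|---|
| Hypothesis Testing | not mentioned | primary |
| Table 1 | primary | secondary |
| Primary and Secondary Outcomes sections | primary | secondary |
| Objectives | Aim 1, not labelled primary | Aim 2, not labelled secondary |
| Abstract | – | the study question |
| Background, last paragraph | the study question | – |

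Each version has support elsewhere, and no sentence settles the matter.

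**2. False-positive chance if any of the five measures may count**

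Inputs: N = 30 (Statistical Analysis) and parallel arms (Study Design, Design). Assumed, because the documents do not say: 15 per arm, two-sided 0.05 per test, one score per measure, no true effect. The five measures are CAARS-S:L, ASRS, PASAT, CPT and Risk Task.

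If the tests are independent, the chance is 1 − 0.95^k:

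- symptom pair, k = 2: 1 − 0.9025 = 9.75%
- three tasks, k = 3: 1 − 0.8574 = 14.3%
- all five, k = 5: 1 − 0.7738 = 22.6%

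With correlated measures (simulation of 400,000 null trials, two-sample t-test, 28 df), all five give:

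| Common correlation | 0.3 | 0.5 | 0.7 | 0.9 |
|---|---|---|---|---|
| Chance of at least one false positive | 21.1% | 18.6% | 15.1% | 10.3% |

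With correlation 0.7 within each set, all five give 18.0% if the between-set correlation is 0.3, and 18.5% if it is 0. More than one score per measure would raise all of these.

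**3. What the contradiction adds by itself**

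At 0.7 within and 0.3 between sets, the symptom pair alone gives about 8.4% and the three tasks alone about 11.1%. Being free to use either set therefore adds 18.0 − 8.4 = 9.6 points over the symptom pair, or 18.0 − 11.1 = 6.9 points over the tasks. The rest is multiplicity within a set.

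**4. The power sentence**

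The plan's figure of about 80% cannot be reproduced from its own inputs. As a range, take 15 per arm and two-sided 0.05, and solve the noncentral t distribution for 80% power with noncentrality d / √[(2/15)(1 − r²)], where r is the baseline-to-final correlation.

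- No baseline adjustment (28 df): d = 1.06. Power is 26% at d = 0.5 and 56% at d = 0.8.
- Baseline-adjusted (27 df), close to 1.06 × √(1 − r²):

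| Assumed r | 0.5 | 0.7 | 0.8 | 0.89 |
|---|---|---|---|---|
| Detectable d | 0.92 | 0.76 | 0.64 | 0.48 |

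The 0.89 is the test-retest value reported for CAARS-S:L in the Primary Outcomes section ("The scale has good internal consistency (Cronbach's alpha .86-.92) and test-retest reliability"). The correlation over four weeks in this trial may be lower. The adjusted figures approximate a model with one baseline and one final value; they are not a power calculation for a mixed model that uses every visit.

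**The case against.** The strongest reply is that the text leans towards symptoms. Table 1, both outcome sections, the order of the aims and the closing sentence of the Background agree, leaving only the Hypothesis Testing paragraph and the abstract on the side of cognition. That is a fair count. But the dissenting paragraph is the one that governs the analysis, the aims carry no ranking, and choosing symptoms would still leave the score unnamed.

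A second reply is that the five-measure figures mix two things, since some multiplicity would remain after the contradiction is removed. This stands in part: the contradiction alone accounts for roughly 7 to 10 points in the block-correlation case. The five-measure figure is still the right description of the plan as written, because both the set and the score are open.

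Third, the power material is a separate matter and shows no error. It is true that about 80% power is attainable under some of the assumptions above and not under others. The claim here is only that the figure cannot be checked until an outcome is named.

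Fourth, a proof-of-concept study need not carry a formal multiplicity scheme. One named score would make such a scheme unnecessary. However, this plan itself declares primary outcomes, hypothesis tests and a power level.

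Last, the Risk Task wording describes what varies in the choices offered more than it defines outcome scores. It does name two kinds of discounting, but the CAARS-S:L subscales are the firmer evidence that no score is fixed.

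**Conclusion.** The concern holds and must be fixed. The primary outcome is defined in two incompatible ways in the current text, and no score is specified under either. This conclusion rests on the text alone and needs no numerical assumption.

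The size does rest on assumptions. With 15 per arm, two-sided 0.05 per test and one score per measure, the five-measure false-positive chance runs from 10.3% (correlation 0.9) to 22.6% (independent). Even the lowest is about twice the nominal 5%. The stated power is uncheckable, which is not the same as shown to be wrong: the detectable standardised difference at 80% power runs from 1.06 down to 0.48, depending on the baseline correlation of whichever outcome is chosen.

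**What to change.** Before unblinding:

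1. Choose one set as primary (the sponsor's decision) and make Table 1, the Primary and Secondary Outcomes sections and the Hypothesis Testing paragraph agree. If symptoms are chosen, the existing headings already fit, and the main edits are to the Hypothesis Testing paragraph and to name the score.
2. Name one primary score, or a small set with a stated multiplicity rule. Define the test as active versus sham at Session 20 using the baseline value, within the planned mixed model, at a stated alpha.
3. If cognition is chosen, replace the open task list in Procedures with the exact task and score.
4. Label the remaining measures as secondary and not multiplicity-controlled.
5. Restate the power sentence for the named score, with a numeric effect size, alpha, allocation ratio and assumed baseline correlation.
6. If a symptom scale is chosen, align the Baseline visit list, whose questionnaire item names only POMS, with Table 1, which marks both scales at Baseline.

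The cost is a wording amendment and one recalculated sentence; the visit schedule in Table 1 does not change. N can remain 30 provided the sponsor accepts the power or detectable effect that results, which may look less favourable than now. Fewer results could be called confirmatory.

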## **3. Confidentiality**

Confidentiality of the data generated in this study shall be maintained in the following ways:

1. All participant information will be kept in a secure filing cabinet that is accessible only to authorized study personnel.
2. All databases containing participant information will be password protected, and again, accessible only to authorized study personnel.

3. Any study communications made by e-mail will use ID numbers only and never include names or any other personal information.
4. All data sets will use ID numbers only. A separate data set subject map table linking names with ID numbers will be accessible only by authorized personnel.

Since self-report and biological data will be collected and stored as part of this study, it is possible that subject privacy or confidentiality can be threatened. To address this concern, the data management system has set up several safeguards to prevent unauthorized access to participant data. In the subject map table, an automatically generated index number is assigned to a subject's study identification number. A linked subject identification table is created to store subject name, address, and telephone contact information. This table uses the automatically generated index number rather than the study identification number. The master subject map and subject identification information are maintained in separate locations. Using this method, no identifying subject information is directly linked to bio-samples or results. All electronic data are stored on institutionally secured and managed network drives. Any publication of data will not identify participants by name or with an identifier that could be used to reveal identity.

All subject data that can be linked to the study ID will be stored in the secure data management system, which has limited, password-required access. The aforementioned precautions and procedures will be applied to protecting subject privacy and the protected health information detailed in Section 4 below.

#### **4. Subject Privacy/Protected Health Information**

The following protected health information (PHI) may be collected as part of this study:

1. Name
2. Street address, city, county, zip code
3. All elements of dates (except year) for dates directly related to an individual and all ages over 89
4. Date of birth
5. Social Security Number
6. Telephone number, email address
7. Results from all questionnaires, tests, and procedures
8. Any other unique identifying number, characteristic, or code

Potential participants will be contacted over the phone after responding to recruitment efforts. Only individuals who have responded to recruitment efforts or who have agreed to be contacted regarding research studies at our Center will be contacted. If an individual cannot be reached immediately, staff members will identify themselves only as calling from the University of Pennsylvania; no mention will be made of the inquiry regarding study participation. Participants will undergo an initial phone screening where preliminary eligibility for the research study will be determined. Only if a participant is initially eligible, will they attend an in-person Intake Visit to confirm eligibility. All data collected over the phone and during in-person visits will be collected by research staff that have completed the CITI-Protection of Human Subjects Research Training as well as HIPAA Compliance Training. Information will never be recorded with identifiers other than study ID. A separate list of names with ID numbers will be accessible only by authorized personnel. All testing, TMS sessions, medical and psychiatric interviews will be conducted individually in dedicated testing and evaluation rooms to protect participant privacy. All records will be kept in locked filing cabinets to maintain confidentiality. Results will not be communicated to other personnel or to the subjects. All analyses will be conducted on de-identified data. Data will be accessible to the Study Investigators, Study Physician, study staff, UPenn IRB, Office of Clinical Research and authorized UPenn staff (e.g. accounting and billing matters, provide treatment, etc.).

## **5. Tissue Specimens**

Urine: Urine (~30ml) will be collected to conduct a urine drug screen and urine pregnancy screen (females only). These samples will be disposed of following the conclusion of every study visit.

## **6. Genetic Testing**

Not Applicable.

## **RISK/BENEFIT ASSESSMENT**

### **1. Potential Study Risks**

The potential risks to participants, and their likelihood and seriousness, are described below. Participants can choose, as an alternative, to not enroll in this study. Overall, there is minimal risk for serious adverse reactions as a consequence of enrolling in this study. Adverse reactions will be assessed and reported as required by Federal law and UPenn regulations.

TMS: The most common adverse effect from TMS is brief and mild muscle contraction headache. This occurs in approximately 10% of subjects. The most significant risk is a seizure. Using single pulse and 1 Hz repetitive TMS no seizures have been reported when stimulus parameters of intensity and duration were within the guidelines described by Wassermann (1998). Similarly, there have been no seizures reported using the brief train at 10 Hz paradigm. These TMS paradigms have been employed at the University of Pennsylvania without any adverse effects. It is also of note that seizures induced by TMS have typically been focal motor seizures. There have been no episodes of status epilepticus; there have been no reports of a TMS associated seizure leading to the development of epilepsy.

A report by Zangen et al. (2005) describes a subject who developed permanent hearing loss after 1 Hz TMS at 120% of the motor threshold; the subject's ear protection had become displaced during the session. This event is of clear concern and relevance to our participants. We will ask participants to immediately report any loosening or detachment of their earplugs or change in the subjective loudness of the coil noise during TMS. Should participants report a change in the sound intensity or feeling that their earplug is displaced, TMS will be immediately terminated until the earplug is repositioned. Additionally, research staff administering TMS will monitor the status of the participant's earplugs and will terminate TMS if the earplugs appear to be displaced on the basis of visual inspection.

There is no need for routine follow-up after a TMS session as side-effects typically occur during the stimulation period. All participants will be given a copy of their signed consent form on which contact information is provided, and will be encouraged to call the project manager, PI or study physician should they have any questions.

Withdrawal Syndrome: Some individuals who discontinue use of stimulant medications (such as Ritalin or Adderall) exhibit a pattern of symptoms related to withdrawal (Ashton et al., 2006; Godfrey 2009; Kutcher et al., 2004). These symptoms include: poor sleep, irritability, fatigue, headaches, depression, and/or return of ADHD symptoms. Eliminating the risk for these would not be possible, although in most cases these events are short-lived and have low intensity. Study personnel will be trained to recognize these symptoms and educate the participants about them (e.g., their duration, methods for reducing them).

Email Communications: In this research study participants may prefer to receive appointment reminders via email or submit questions related participation via email. Email is not a secure means of communication. Email messages travel across the Internet passing through multiple

computers before reaching their final destination. It is not possible to know whether an email a participant sends will be viewed along the way. Additionally, if sent messages are not deleted, an email provider may have an archive of everything that is sent. If someone gets access to an email account (for example, a participant's family member), they could see archived messages. There are many other ways in which emails are not secure—these are only selected examples. To manage this risk the informed consent form will include specific language to educate research participants on the privacy risks involved in email communications. Participants will also be explicitly instructed to only use email communications for routine matters and never for personal or confidential messages or questions.

Threats to Privacy/Confidentiality: See description in Section 3 (Confidentiality) and 4 (Subject Privacy/Protected Health Information) above.

